1.0 PROTOCOL SUMMARY AND/OR SCHEMA

This is a phase 2, open-label, non-randomized study evaluating the novel combination of pembrolizumab and olaparib (POLAR) for maintenance therapy in three cohorts of metastatic PDAC patients with homologous recombination deficiency (HRD) in the first-line or second-line on-platinum setting; two cohorts are genomically enriched and one cohort is identified by platinum sensitivity. The primary endpoint of this study is to evaluate the co-primary endpoints using either 6-month progression-free survival (PFS) rate and objective response rate (ORR) of this combination. The secondary endpoints of this study are overall survival (OS), progression-free survival (PFS), disease control rate (DCR), CA 19-9, and CEA response. Statistically powered analysis of co-primary endpoints will be assessed in Cohort A only and other clinical endpoints will be descriptive in Cohort B and C. Exploratory scientific correlates include assessments of HRD genetic mutational signatures, neoantigens, immunogenic tumor microenvironment, and clonal evolutionary dynamics to study heterogeneity and resistance mechanism to POLAR.

Patients will be assigned to cohorts. Cohorts will be defined as following by CLIA-approved NGS or MSK-IMPACT Part A or C:

[figure not shown]
- **Cohort A**: Patients with either pathogenic germline or somatic alterations of 3 core homologous recombination-genes (HR-genes) (*BRCA1/2*, or *PALB2*) who have stable or responding disease on first-line or second-line platinum therapy in two consecutive imaging assessments over at least 4 months or 16 weeks are eligible for inclusion in Cohort A.
- Cohort B: Patients with either pathogenic somatic or germline non-core 15 HR-gene alterations (ATM, BAP1, BARD1, BLM, BRIP1, CHEK2, FAM175A, FANCA, FANCC, MUTYH, NBN, RAD50, RAD51, RAD51C, RTEL1) who have stable or responding disease on first-line or second-line platinum therapy in two consecutive imaging assessments over at least 4 months are eligible for inclusion in Cohort B.

POLAR: a phase 2 trial for pembrolizumab and olaparib maintenance for metastatic PDAC and HRD and/or Exceptional Response to Platinum – Ver. 5/3/2020

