• Cohort C: Patients without any of the above HR-gene alterations included in Cohort A and B who have platinum-sensitivity, which is defined as durable response of either a partial response (PR) or complete response (CR) during at least 6 months on platinum-based therapy. Variants of unknown significance of candidate HR-genes from Cohort A or B will be eligible for Cohort C if they meet the partial response to platinum criterion.

All the participating patients will receive the combination of pembrolizumab 200 mg IV every 3 week and olaparib 300 mg twice day orally daily continuously (POLAR) as a maintenance therapy. After the first 6 months (9 cycles), on C10D1 Pembrolizumab 400 mg IV every 6 week plus olaparib 300 mg twice a day orally will be continued. Per treating investigator's discretion, patients may remain at Pembrolizumab 200 mg IV every 3 weeks after the first 9 cycles. Additionally, to accomodate patients traveling far distances, if, per treating investigator, after the first or second imaging, there are no toxicities, patient's dosing of Pembrolizumab may change to 400 mg IV every 6 weeks. All cycles will be 21-days (3 weeks) in length.

Figure 1. Schema for Genetic and Response Eligibility Criteria:

Number of trial participants	63 (Cohort A: 33, Cohort B: 15, Cohort C: 15)
Estimated enrolment period	3 years
Estimated duration of trial	7.5 years
Duration of Participation	4 years

Estimated average length of	4 months
treatment per participant	

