2.0 OBJECTIVES AND SCIENTIFIC AIMS

Primary Objective:

- For Cohort A: To evaluate the activity of pembrolizumab and olaparib (POLAR) combination by co-primary endpoints using either radiographic 6-month PFS rate by RECIST v1.1 and ORR using iRECIST in metastatic pancreas adenocarcinoma (PDAC) patients with core HR-gene mutations.
- For Cohort B and C: To exploratively evaluate the activity of POLAR combination by radiographic ORR using RECIST 1.1.

Secondary Objectives:

- To assess the safety of POLAR by grading adverse events (AE) using CTCAE v. 5.0.
- To assess activity of POLAR by measuring disease control rate (DCR) by both RECIST v1.1 and iRECIST, best overall response rate (BOR), progression-free survival (PFS) by both RECIST v1.1 and iRECIST, overall survival (OS), CEA, and CA 19-9 response. Progression-free survival (PFS) will be analyzed from both the consent date and treatment start date (C1D1) (Reference study POLO defined PFS from the time of randomization not from C1D1, Golan 2019 NEJM).

Exploratory Objectives:

- To explore genetic and transcriptomic signatures for POLAR sensitivity and resistance from HRD Cohort A and B as well as from the platinum-sensitivity Cohort C.
- To describe neoantigen induction, the immunogenic tumor microenvironment (TME), and describe putative immunomodulatory targets from each cohort.
- To explore resistance mechanisms and the role of spatiotemporal heterogeneity by evaluating the tumor samples and circulating tumor DNA (MSK-ACCESS)
- To develop a biorepository of organoids and prospectively evaluate organoids concurrently with the trial in select patients.
- To assess second progression-free survival (PFS2) from time of subsequent systemic treatment start post-POLAR to progression on that treatment.
- To assess duration of the first-line or second-line treatment prior to POLAR treatment.
- To assess genetic signatures and compare clinical outcomes (ORR, PFS, OS) for patients with PDAC harboring specific HRD-gene mutations such as BRCA1, BRCA2, PALB2, ATM, and no HRD-gene mutation.
- To assess the association of other non-HRD gene mutations (such as KRAS allelic imbalance, TP53, SMAD4, CDKN2A homozygous deletion) with the clinical outcomes.
- Evaluate reversion mutation, zygosity, plasticity, and aneuploidy from tumor and circulating tumor DNA.

Confidential

POLAR: a phase 2 trial for pembrolizumab and olaparib maintenance for metastatic PDAC and HRD and/or Exceptional Response to Platinum – Ver. 5/3/2020

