We will determine the immunologic role of synthetic lethality in metastatic PDAC with HRD and evaluate for improvement in clinical outcome with different degrees of synthetic lethality anticipated in different cohorts when treated with POLAR. The three cohorts are as following. Cohort A will include patients with either pathogenic germline or somatic alterations of 3 core homologous recombination-genes (HR-genes) - (BRCA1/2, or PALB2) and have stable or responding disease on first-line or second-line platinum therapy in two consecutive imaging assessments over at least 4 months or 16 weeks. Cohort B will include patients with non-core 15 HR-gene alterations (ATM, BAP1, BARD1, BLM, BRIP1, CHEK2, FAM175A, FANCA, FANCC, MUTYH, NBN, RAD50, RAD51, RAD51C, RTEL1) and have stable or responding disease on first-line or second-line platinum therapy in two consecutive imaging assessments over at least 4 months. Cohort C will include patients without any of the above HR-gene alterations included in Cohort A and B who have platinum-sensitivity, which is defined as a partial response (PR) or complete response (CR) for the best overall response (BOR) during at least 6 months on platinum-based therapy. Variants of unknown significance of candidate HRgenes from Cohort A or B will be eligible for Cohort C if they meet the partial response to platinum criterion. Of note, patients will be assigned and not randomized to Cohorts A, B and C.

All participating patients in the three cohorts will receive the combination of pembrolizumab 200 mg IV every 3 week and olaparib 300 mg twice day orally daily (POLAR) as maintenance therapy. After the first 6 months (9 cycles), on C10D1 Pembrolizumab 400 mg IV every 6 week plus olaparib 300 mg twice a day orally will be continued. Per treating investigator's discretion, patients may remain at Pembrolizumab 200 mg IV every 3 weeks after the first 9 cycles. Additionally, to accomodate patients traveling far distances, if, per treating investigator, after the first or second imaging, there are no toxicities, patient's dosing of Pembrolizumab may change to 400 mg IV every 6 weeks. All cycles will be 21-days (3 weeks) in length. The correlation of the immunogenomic landscape and spatiotemporal heterogeneity with clinical response to POLAR will provide an opportunity to develop genomic biomarkers and gather insights into resistance mechanism to POLAR.

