4.0 OVERVIEW OF STUDY DESIGN/INTERVENTION

4.1 Design

This is a phase 2 open-label, non-randomized 3-cohort study to evaluate the safety and clinical efficacy of a novel combination - pembrolizumab and olaparib (POLAR) in genomically enriched three cohorts of metastatic PDAC patients with homologous recombination deficiency (HRD) as below.

Patients will be assigned to cohorts. Cohorts will be defined as following by CLIA-approved NGS or MSK-IMPACT Part A or C:

- **Cohort A**: Patients with either pathogenic germline or somatic alterations of 3 core homologous recombination-genes (HR-genes) (*BRCA1/2*, or *PALB2*) who have stable or responding disease on first-line or second-line platinum therapy in two consecutive imaging assessments over at least 4 months or 16 weeks are eligible for inclusion in Cohort A.
- Cohort B: Patients with either pathogenic somatic or germline non-core 15 HR-gene alterations (ATM, BAP1, BARD1, BLM, BRIP1, CHEK2, FAM175A, FANCA, FANCC, MUTYH, NBN, RAD50, RAD51, RAD51C, RTEL1) who have stable or responding disease on first-line or second-line platinum therapy in two consecutive imaging assessments over at least 4 months are eligible for inclusion in Cohort B.
- Cohort C: Patients without any of the above HR-gene alterations included in Cohort A and B who have platinum-sensitivity, which is defined as a partial response (PR) or complete response (CR) for the best overall response (BOR) during at least 6 months on platinum-based therapy. Variants of unknown significance of candidate HR-genes from Cohort A or B will be eligible for Cohort C if they meet the partial response to platinum criterion.

All the participating patients will receive the combination of pembrolizumab 200 mg IV every 3 week and olaparib 300 mg twice day orally daily continuously (POLAR) as a maintenance therapy. After the first 6 months (9 cycles), on C10D1 Pembrolizumab 400 mg IV every 6 week plus olaparib 300 mg twice a day orally will be continued. Per treating investigator's discretion, patients may remain at Pembrolizumab 200 mg IV every 3 weeks after the first 9 cycles. Additionally, to accomodate patients traveling far distances, if, per treating investigator, after the first or second imaging, there are no toxicities, patient's dosing of Pembrolizumab may change to 400 mg IV every 6 weeks. All cycles will be 21-days (3 weeks) in length.

[figure not shown]

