6.0 CRITERIA FOR PARTICIPANT ELIGIBILITY

6.1 Participant Inclusion Criteria

This is an on-platinum maintenance trial either in a first-line or second-line setting.
 Participants must have either stable disease or responding disease on current first-line or second-line platinum treatment for metastatic disease.

0

POLAR: a phase 2 trial for pembrolizumab and olaparib maintenance for metastatic PDAC and HRD and/or Exceptional Response to Platinum – Ver. 5/3/2020

2. Male or female patients with cytologically or histologically confirmed metastatic pancreas adenocarcinoma or acinar cell carcinoma with homologous recombination gene alterations or platinum sensitivity as per following cohort inclusion criteria below.

Patients will be assigned to cohorts based on their genetic alterations and clinical response. Patient stratification to different Cohorts will be in the order of more canonical homologous recombination-gene (HR-gene) order. For example, patients who meet criteria for both A and B Cohorts, they will be assigned to Cohort A, not B. Cohorts will be defined as following by CLIA-approved NGS or MSK-IMPACT Part A or C:

- Cohort A: Patients with either pathogenic germline or somatic alterations of 3 core HR-genes
 (BRCA1/2, or PALB2) who have stable or responding disease on first-line or second-line platinum therapy in two consecutive imaging assessments over at least 4 months or 16 weeks are eligible for inclusion in Cohort A.
- Cohort B: Patients with either pathogenic somatic or germline non-core 15 HR-gene alterations (ATM, BAP1, BARD1, BLM, BRIP1, CHEK2, FAM175A, FANCA, FANCC, MUTYH, NBN, RAD50, RAD51, RAD51C, RTEL1) who have stable or responding disease on first-line or second-line platinum therapy in two consecutive imaging assessments over at least 4 months are eligible for inclusion in Cohort B.
- Cohort C: Patients without any of the above HR-gene alterations included in Cohort A and B who have platinum-sensitivity, which is defined as a partial response (PR) or complete response (CR) for the best overall response (BOR) during at least 6 months on platinumbased therapy. Variants of unknown significance of candidate HR-genes from Cohort A or B will be eligible for Cohort C if they meet the partial response to platinum criterion.

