Wilcoxon rank sum test will be used to assess associations between genetic and transcriptomic signatures at baseline with response while Cox regression will be used to assess associations with PFS and OS. These analyses will be conducted separately for each cohort acknowledging the exploratory nature of these analyses particularly for Cohorts B and C which have limited sample size. Changes between baseline and after treatment in neoantigen induction, TME, and immunomodulatory targets will be summarized descriptively using medians and interquartile range for each cohort separately. To understand the resistance mechanisms, post-treatment changes (4-6 weeks and at progression) of tumor samples and circulating tumor DNA (MSK-ACCESS) from baseline will be associated with response using Wilcoxon rank sum test while Cox regression will be used for PFS and OS outcomes. Finally, in selected patients with viable organoids available from IRB# 15-149 prior to enrollment to POLAR trial, we will concurrently evaluate the response of organoid to POLAR in real time as participants are treated in parallel. Dr. [name] will oversee this part. PFS2 will be estimated using the Kaplan-Meier method. Associations between genetic mutations (HRD and non-HRD) and outcome will be assessed using Fisher's exact test for response and log-rank test for survival outcomes. Biomarkers (reversion mutation, zygosity, plasticity, aneuploidy from tumor, and circulating tumor DNA) will be summarized using proportions. Presence of circulating tumor DNA and levels of CA 19-9 prior to treatment at time points prior to consent and between the consent and start date will be graphically summarized at each timepoint.

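### The exploratory comparison of HRD-gene carriers with patients who have no HRD-gene mutation is confounded by the cohort entry rules

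*Protocol*

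**What the plan says.** Section 2.0 lists, as an exploratory objective, to "compare clinical outcomes (ORR, PFS, OS) for patients with PDAC harboring specific HRD-gene mutations such as BRCA1, BRCA2, PALB2, ATM, and no HRD-gene mutation". Section 14.0 (Exploratory objectives) supplies the method: "Associations between genetic mutations (HRD and non-HRD) and outcome will be assessed", with Fisher's exact test for response and the log-rank test for survival outcomes. It names no stratification, covariate or restriction for this comparison.

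The groups enter under different platinum rules:

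- **Cohort A** (BRCA1/2, PALB2), Section 6.1: "stable or responding disease on first-line or second-line platinum therapy in two consecutive imaging assessments over at least 4 months or 16 weeks".
- **Cohort B** (ATM and the other non-core genes), Section 1.0: stable disease or a response on "platinum therapy in two consecutive imaging assessments over at least 4 months are eligible for inclusion in Cohort B".
- **Cohort C** (none of those alterations), Section 6.1: platinum sensitivity, "defined as a partial response (PR) or complete response (CR) for the best overall response (BOR) during at least 6 months". Section 4.1 agrees. Section 1.0 words it as a "durable response of either a partial response (PR) or complete response (CR) during at least 6 months on platinum-based therapy".

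The planned sizes are 33, 15 and 15 (Section 1.0). PFS and OS run from the start of study treatment (Section 13.1). Section 3.3 says that the trial will "evaluate for improvement in clinical outcome with different degrees of synthetic lethality anticipated in different cohorts". The difference in entry rules is nowhere mentioned as a limit on the carrier versus non-carrier comparison.

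**The concern.** A comparison by gene status is informative only if the groups are otherwise reasonably alike, or if the differences can be adjusted for. Here eligibility makes them unlike in depth and length of prior platinum response. The protocol itself treats that feature as prognostic: Section 3.3 justifies a maintenance trial in platinum-sensitive disease by noting that platinum-refractory patients resisted PARP inhibition even with a BRCA mutation.

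At stake is the reading of one exploratory result. A true advantage of HRD-gene carriers in PFS or OS could be shrunk or hidden by the entry rule, and a difference could appear where gene status has no effect. More patients would not help, because this is bias and not imprecision.

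**Working it through.** **1. Is there a figure in the plan to reproduce?** None is given for this comparison. The only powered calculation is the Cohort A two-stage design. It reproduces (type I error 0.028 for PFS and 0.020 for ORR, power 81% for each) and is not an input here.

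**2. Overlap of gene status and entry rule.**

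| | HRD-gene carriers | No HRD-gene mutation |
|---|---|---|
| Route of entry | Cohorts A and B | Cohort C only |
| Planned number | 33 + 15 = 48 | 15 |
| Stable disease on platinum allowed | yes | no |
| Minimum time on platinum | 4 months | 6 months |

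The no-mutation column has no stable-disease stratum. Stratifying or adjusting by best platinum response would leave the carriers with stable disease nothing to be compared with. The data cannot separate gene status from the entry rule across the full groups. Contrasts among BRCA1, BRCA2, PALB2 and ATM stay inside Cohorts A and B, whose rules are essentially the same, so they escape the problem.

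**3. Direction.** For PFS and OS, selection on a deeper and longer platinum response probably favours the no-mutation group whatever its genes. For ORR two forces oppose each other. Sections 6.1 and 13.2 admit patients with no measurable disease, and patients in complete response, who have little or no room for a new response. On the other hand, strong platinum responders may be more sensitive to a PARP inhibitor. The net direction cannot be told.

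**4. Size, by illustration.** These inputs are assumptions; the protocol gives none of them. Let pR be the 6-month PFS rate in patients who meet the Cohort C platinum criterion, pS the rate in other carriers, and q the share of carriers who meet it. With no gene effect:

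- carriers: q·pR + (1 − q)·pS
- no mutation: pR
- false difference favouring no mutation: (1 − q)·(pR − pS)

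| pR / pS | q = 0.3 | q = 0.5 | q = 0.7 | q = 1 |
|---|---|---|---|---|
| 60% / 50% | 7 points | 5 | 3 | 0 |
| 70% / 40% | 21 points | 15 | 9 | 0 |
| 75% / 35% | 28 points | 20 | 12 | 0 |

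In the middle row, a two-sided 5% Fisher's exact test on 48 against 15 patients, with 6-month PFS taken as binary, rejects in 25%, 14% and 7% of trials. At q = 1, where every carrier meets the criterion, it rejects in about 3% (still with 48 carriers).

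**5. Masking.** Assume a true 20-point advantage for carriers: 80% in carriers meeting the criterion and 50% in other carriers, against 60% in Cohort C. The expected observed difference is 0.8q + 0.5(1 − q) − 0.6:

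- q = 0.3: 0.24 + 0.35 − 0.60 = −1 point
- q = 0.5: 0.40 + 0.25 − 0.60 = +5 points
- q = 0.7: 0.56 + 0.15 − 0.60 = +11 points
- q = 1: 0.80 − 0.60 = +20 points, the true value

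**The case against.** The case for leaving the text alone is a fair one.

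- **The objective is exploratory.** No decision or stopping rule rests on it, Section 1.0 calls clinical endpoints in Cohorts B and C descriptive, and Section 14.0 admits the limited sample size. This limits the severity. It does not excuse a systematic bias, and Section 14.0 goes beyond description by naming tests.
- **The different entry rules are deliberate.** Section 3.3 enrols by genotype and by platinum-sensitive phenotype, and suspects undetected repair defects in the second group. That stands: eligibility need not change, and Cohort C was not offered as an HRD-negative control. It is all the more reason not to read the contrast as one.
- **The sentence on tests is ambiguous.** Its reference to HRD and non-HRD mutations may point to two kinds of gene, not to carriers and non-carriers. That is possible, but Section 2.0 names the no-mutation group outright, and no other method is given for it.
- **Analyses run separately by cohort, and details belong in an SAP.** The by-cohort sentence follows the signature analyses and cannot govern groups that never share a cohort. The protocol already fixes both the comparison and its tests.
- **The bias may be smaller than the noise.** With 15 patients the protocol's own margin, stated for DCR, is about 25 points, and most of the illustrated differences are smaller. This is true, and the sizes are assumed.
- **Restriction is not a cure.** Section 3.1 links HR-gene alterations to better outcome on platinum, so platinum response may itself follow from genotype, and restricting conditions on it. This stands and limits what the restricted contrast can claim.

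A reader might infer that every genotype comparison is spoiled, that carriers all enter with stable disease, or that Cohort C's ORR must be pushed down. The documents support none of these: contrasts among the named genes share essentially one rule, Cohorts A and B also admit responders, and the ORR direction is open. Nor does Section 3.3 tie its remark on synthetic lethality to these tests; it speaks of cohorts.

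**Conclusion.** The point holds for one contrast only: any HRD-gene alteration against none, for ORR, PFS and OS. As planned it is wholly mixed with the platinum entry rule, apart from any patient whose gene status changes at the retrospective confirmation described in Section 4.1. The Cohort A primary analysis is not touched.

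The bias probably favours the no-mutation group for PFS and OS. The 3 to 28 points shown above depend on assumed PFS rates and an assumed mix of platinum response among carriers, and on all three cohorts filling. They show what the entry rule can do and are not an estimate of what it will do. A reader might conclude that an HRD advantage will be hidden or reversed; the protocol holds no figure from which that follows. The matter is worth correcting, but its weight is modest because the objective is exploratory.

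**What to change.** Add a paragraph to Section 14.0, Exploratory objectives, for the carrier versus no-HRD-gene contrast:

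1. Compare Cohort C with those Cohort A/B patients who also meet the Cohort C platinum criterion (partial or complete response during at least 6 months of platinum), and make this the comparison that is interpreted. Use one wording of the criterion on both sides; Section 1.0 differs from Sections 4.1 and 6.1 and should be reconciled with them.
2. Report the unrestricted A/B versus C difference descriptively only, and state that it is not a genotype effect.
3. Do not rely on stratification by best platinum response, since Cohort C has no stable-disease stratum.
4. State that the restricted contrast is conditional on platinum response, and so exploratory and not causal.

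No new data should be needed: platinum response is assessed for eligibility, and duration of the preceding treatment is already an exploratory objective in Section 2.0. The cost is precision. If 30%, 50% or 70% of the 48 planned carriers qualify, about 14, 24 or 34 remain against 15.
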